3.1 Treatment Groups

406 Each patient is randomly assigned to one of the two treatment groups:

- 407 • Atropine 1% once each weekend day in the sound eye
- 408 • Atropine 1% once each weekend day in the sound eye plus a plano lens for the sound eye

409

410 For both treatment groups:

- 411 • Atropine is discontinued after 16 weeks (2 weeks prior to visit 8C).
- 412 • If acuity in amblyopic eye becomes the same or better than acuity in the sound eye, the
- 413 frequency of atropine should be maintained through 16 weeks.
- 414 • If reverse amblyopia is suspected or strabismus develops or worsens, treatment is at
- 415 investigator discretion.
- 416 • If an allergy to atropine develops, the patient can be switched to homatropine 5% after
- 417 discussion with a Protocol Chair.

418

419 Notes

- 420 1. The study will be providing atropine drops and sunglasses (or flip-ups) for the patients. The
- 421 dispensing of atropine will be recorded on the ATS Atropine Accountability Log.
- 422 2. Wearing a hat with a brim for outdoor activities is to be encouraged.
- 423 3. Morning is the preferred time for administration of the atropine. However, if there is an
- 424 overriding reason why the parent/guardian wants to administer the atropine at night, this will be
- 425 acceptable.
- 426 4. If a patient is noncompliant with treatment, the parents should be encouraged to persist with the
- 427 treatment to the best of their ability.
- 428 5. Deviations from the treatment protocols or prescribing non-protocol treatment should be
- 429 discussed with a Protocol Chair prior to initiating.
- 430 6. Discontinuation of therapy due to reverse amblyopia, strabismus, or atropine allergy should be
- 431 discussed with a Protocol Chair.
- 432
- 433 7. Both treatment groups will receive atropine in the sound eye, which should help tolerance of
- 434 wear of the full or near-full cycloplegic correction. Therefore, bilateral atropine to relax
- 435 accommodation for two days is not likely necessary, and will not be allowed.

436

437 **3.1.1 Compliance**

438 A calendar log will be maintained by patients on treatment. The preprinted calendar will contain

439 customized instructions about treatment.

- 440 1. An adhesive sticker will be placed by the child on the log on days when the atropine was used.
- 441 2. These logs will be turned in to the investigator at each of the protocol visits. At each visit, the
- 442 logs will be reviewed. The investigator's assessment of compliance will be recorded on the
- 443 Follow-up Examination Form.

444 **3.2 Follow-up Examinations**

445 All patients will have the following study visits:

- 446 • Visit 8A: 5 ± 1 week
- 447 • Visit 8B: 10 ± 1 week
- 448 • Visit 8C: 18 ± 1 week

449
450

| Test | Visit | | |
|-----------------------------|-----------------------|------------------------|------------------------|
| | 8A 5 ± 1 wk | 8B 10 ± 1 wk | 8C 18 ± 1 wk |
| Distance acuity each eye* | X | X | X |
| Binocular distance acuity | | | X |
| Ocular alignment** | | | X |
| Fixation Preference testing | X | | |
| Stereoacuity and fusion*** | | | X |

451 *using ATS single-surround HOTV acuity testing protocol on the EVA. The testing at visit 8C will
 452 be done by a masked examiner
 453 **Assessed at each visit but only quantified at visit 8C after atropine discontinued (at other visits, the
 454 development of a new or increased deviation will be reported)
 455 ***Titmus fly, Randot Preschool Test, and Randot Suppression Test

456

457 Additional visits can be performed at the discretion of the investigator. A Follow-up Examination
 458 Form should be completed on the study website for every exam (not just the minimum required
 459 exams).

460

461 Two weeks prior to visit 8C (18 weeks) after 16 weeks of treatment, atropine treatment will be
 462 discontinued in all patients. The parents of patients who were randomized to receive atropine plus a
 463 plano lens will be instructed to bring the old glasses to a visit prior to 8C, which will be used during
 464 the outcome exam.

465

466 **3.2.1 Visual Acuity Testing**

467 At each visit, visual acuity is measured in each eye (right eye first) by a certified examiner using the
 468 ATS single-surround HOTV acuity protocol on the Electronic Visual Acuity Tester.

- 469 • While atropine is being used, the sound eye will be tested with the full cycloplegic
 470 correction in trial frames.

- 471 • The visual acuity measurement at visit 8C (18 weeks) will be done by a masked
 472 examiner.

473

474 **3.2.2 Fixation Preference Testing**

475 At visit 8A (5 weeks), a test of fixation preference at near under the treatment conditions will be
 476 conducted after acuity testing. The procedures for the strabismic and non-strabismic patients are
 477 described in the PEDIG procedures manual.

478

479 **3.2.3 Visit 8C Exam**

480 Visit 8C will occur at 18±1 week, 2 weeks after the discontinuation of atropine.

481

482 The parents of patients who were randomized to receive atropine plus a plano lens will be instructed
 483 to bring the old glasses to a visit prior to 8C. The old glasses used at enrollment will be retained at
 484 the site and used during the outcome exam. They will be returned to the family at the end of the

485 study. If a plano group patient's refraction has changed in the sound eye prior to visit 8C, visual
486 acuity may be tested in trial frames with the new correction instead of the enrollment glasses.
487 In addition to visual acuity testing, testing will include the following:

- 488 • Titmus fly and Randot Preschool test
- 489 • Randot Suppression Test
- 490 • Binocular distance acuity
- 491 • Ocular alignment assessed with the SPCT
- 492 • Retesting of visual acuity in the amblyopic eye
 - 493 ○ Only performed if visual acuity is worse than 20/25, acuity is not improved from
 - 494 baseline by at least 2 lines, or acuity is not improved from the last visit by at least
 - 495 one line
- 496 • Retesting of visual acuity in the sound eye
 - 497 ○ Only performed if the sound eye acuity is reduced by 1 or more lines from its
 - 498 baseline acuity.
 - 499 ○ If it is still decreased after retesting, then a cycloplegic refraction should be
 - 500 performed, lenses adjusted in trial frames/phoropter, and then the acuity should
 - 501 be tested again, modifying the refractive correction in trial frames if indicated.
 - 502 ○ If acuity is still reduced by one or more lines from pretreatment baseline and
 - 503 there has been a change in refraction from the spectacle wear, a change in
 - 504 spectacle lens should be prescribed (*the study will pay for this change*).
 - 505 ○ If the best sound eye acuity at visit 8C is decreased 1 or more lines from baseline
 - 506 (and worse than 20/20), the patient should return in 1 to 4 weeks (visit 8C-2) to
 - 507 recheck the sound eye acuity (with the new spectacles, if a change was
 - 508 prescribed). The patient should remain off atropine and should not start any
 - 509 other amblyopia therapy for either eye.
 - 510

511 Patients who have not discontinued atropine at least 2 weeks prior to visit 8C may use the
512 enrollment correction or the full cycloplegic correction for the testing of the sound eye. All
513 binocularity testing must be done in trial frames correcting the residual hypermetropic deficit plus
514 +3.00D to account for the near distance in the atropinized eye.
515

516 **3.3 Additional Follow-up for Partial Responders**

517 After visit 8C, follow up will end for all patients except for the patients who meet both of the
518 following criteria:

- 519 • amblyopic eye acuity (better of test and retest, if done) worse than 20/25, improved 2 or
520 more lines from baseline and improved at least one line from visit 8B (if missed, then
521 one line from 8A)

522 AND

- 523 • amblyopic eye acuity worse than best visit 8C (18 weeks) sound eye acuity
524

525 Patients continuing in follow up will resume using the randomized treatment (for patients in the
526 'plano' group, the spectacles with the plano lens will continue to be used) and will have a follow-up
527 visit every 8± 1 weeks until:

- 528
- 529 (1) amblyopic eye acuity reaches 20/25 or better,
- 530 (2) treatment is discontinued because the sound eye worsened, or
- 531 (3) there is no further improvement in the amblyopic eye acuity.

- 532
- ‘No further improvement’ is defined as visual acuity in the amblyopic eye that is no
- 533 better than the measured acuity at the prior visit on two tests of acuity at the same visit.
- 534 At the first 8-week visit, the better amblyopic eye acuity at visit 8C is used as the
- 535 ‘baseline’ for evaluating improvement. At subsequent visits, the acuity from the prior
- 536 visit is used (or better acuity if acuity was tested twice at that visit).
- 537

538 At each visit, distance visual acuity will be measured in each eye using the ATS single-surround

539 HOTV acuity protocol on the Electronic Visual Acuity Tester. If the amblyopic eye acuity is not

540 improved by 1 or more lines from the prior visit, the visual acuity test will be repeated.

541

542 For patients remaining in the study after 6 months from enrollment, a cycloplegic refraction is

543 encouraged.

544

545 When study participation ends for patients in the ‘plano’ group, the plano lens in their study-paid

546 spectacles may be replaced with a lens of proper correction purchased by the study.

547
548
549
550
551
552
553
554
555
556
557
558
559
560
561
562
563
564
565
566
567
568
569
570
571
572
573
574
575
576
577
578
579
580
581
582
583
584
585
586
587
588
589
590
591
592

Chapter 4: MISCELLANEOUS CONSIDERATIONS

4.1 Management of Optical Correction

A refraction should be performed at any time the investigator suspects that refractive error may not be optimally corrected.

4.2 Management of Strabismus

Strabismus surgery is allowed at the discretion of the clinician. These will be recorded in the comment section of the Follow-up Examination Form.

4.3 Intercurrent Events

If visual acuity should worsen in the amblyopic eye (or in the sound eye and does not recover with cessation or reversal of treatment), the investigator should evaluate this condition using best clinical judgment and perform whatever work up is clinically indicated to assess for an alternate cause (i.e., other than amblyopia) for the visual loss. Patients found to have a cause other than amblyopia that fully explains the visual loss (i.e., amblyopia was never present) will be dropped from the study. This will be reported on the Patient Final Status Form.

Eye injuries or the development of an eye problem that might affect vision will be reported on the Follow-up Examination Form. Likewise, the development of a serious medical problem that might affect the patient's study participation will be recorded.

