105 prescribing less than full hypermetropic spectacle correction for the sound eye, effectively blurring
106 the eye at near and distance fixation. Some pediatric eye care providers prescribe a plano or
107 reduced-plus lens concurrent with the initiation of atropine treatment believing that this will
108 accelerate the visual improvement and provide a better visual acuity outcome than atropine alone.¹⁰
109 Kaye and colleagues took patients who were failing occlusion therapy after a mean of 36 weeks and
110 prescribed atropine 1% and a plano lens for the sound eye. After 10 weeks they found an
111 improvement in geometric mean acuity from 20/113 to 20/37. In ATS1, a plano lens was prescribed
112 for the sound eye only if the patient had not improved to 20/30 or at least 3 lines after 4 months of
113 daily atropine use.^{1,11} Among the 55 patients in ATS1 who were prescribed a plano lens for the
114 sound eye during follow up, the distance optical blur from the plano lens induced by cycloplegia
115 was >0.50 to ≤1.00 D for 2 patients, >1.00 to ≤2.00 D for 9 patients, >2.00 to ≤3.00 D for 11
116 patients, and >3.00 D for 33 patients. The mean improvement in acuity prior to the use of the plano
117 lens was 1.0 line compared with 1.6 lines after prescribing the plano lens (P=0.11 by paired t-test).
118 While using the plano lens, the amount of improvement was not related to the amount of optical
119 induced blur; patients with induced blur >3.00 D had 1.7 mean lines of improvement and patients
120 with induced blur ≤3.00 D had 1.5 mean lines of improvement (P=0.93 evaluating induced blur as a
121 continuous variable in linear regression model). ATS8 will assess whether prescribing a plano lens
122 concurrently with initiating atropine therapy will produce a faster or a better visual acuity outcome
123 by 17 weeks than prescribing atropine alone.

124
125 In ATS1, a reduction in sound eye visual acuity (2 or more lines) occurred at 6 months more
126 frequently when a plano lens was prescribed in addition to atropine (7 of 43, 16%) compared with
127 treatment with atropine alone (4 of 123, 3%; P=0.01). However, after longer follow-up the sound
128 eye of only one patient treated with atropine alone and no patient treated with atropine plus the
129 plano lens was worse than baseline.

130
131 In ATS4 the use of atropine was associated with the loss of two lines in the sound eye of only 1 of

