272 spherical equivalent, and the reduction in plus sphere must be symmetric in the
273 two eyes. Otherwise, spectacle correction is at investigator discretion.
274
- 275 2) For patients meeting criteria for anisometropia or combined-mechanism (see #2 above)
- 276 • Spherical equivalent must be within 0.50 D of fully correcting the anisometropia
277 • Hypermetropia must not be undercorrected by more than +1.50 D spherical
278 equivalent, and reduction in plus must be symmetric in the two eyes
279 • Cylinder power in both eyes must be within 0.50 D of fully correcting the
280 astigmatism
281 • Cylinder axis in the spectacle lenses in both eyes must be within 6 degrees of the
282 axis of the cycloplegic refraction when cylinder power is ≥ 1.00 D
283
- 284 *Note: if NEW spectacles are being prescribed in anticipation of study enrollment, it is*
285 *advisable to fully correct the anisometropia, fully correct astigmatism, and symmetrically*
286 *reduce the hypermetropic correction by no more than +0.50 D to avoid having to replace*
287 *the lenses immediately following randomization (see section 2.4.2)*
288
- 289 b. Spectacles meeting above criteria must be worn either:
- 290 1) for 16 weeks immediately prior to enrollment, or
291
- 292 2) until visual acuity in amblyopic eye is stable (defined as two consecutive visual acuity
293 measurements by the same testing method at least 4 weeks apart with no improvement
294 of one logMAR line or more)
- 295 • An acuity measurement done any of the following ways may be considered the
296 first of two consecutive measurements: 1) in current glasses , 2) in trial frames
297 with full correction of hypermetropia with cycloplegia, or 3) by having the
298 patient return in new glasses for first measurement. *Note: since this*
299 *determination is a pre-study procedure, the method of measuring visual acuity is*
300 *not mandated.*
301
- 302 8. No current vision therapy or orthoptics
- 303 9. No ocular cause for reduced visual acuity
- 304 • nystagmus per se does not exclude the patient if the above visual acuity criteria are met
- 305 10. Cycloplegic refraction within 6 months prior to enrollment
- 306 11. Ocular examination within 6 months prior to enrollment
- 307 12. No prior intraocular or refractive surgery
- 308 13. No known allergy to atropine or other cycloplegic drugs

- 309 14. Down Syndrome not present
310 15. Parent willing to accept randomized treatment, available for 6 months of follow-up, has home

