350 1. Once a patient is randomized that patient will be included regardless of whether the assigned
351 treatment is received or not. Thus, the investigator must not randomize a patient until he/she
352 is convinced that the parent/guardian will accept either of the treatment regimens.

353 2. Treatment must commence within 48 hours following randomization; therefore, a patient
354 should not be randomized until both the investigator and parent are ready to start treatment.

355 3. The Jaeb Center will construct a separate Master Randomization List for moderate
356 amblyopia and severe amblyopia using a permuted block design stratified by site and by
357 visual acuity (20/40 to 20/100 and 20/125 to 20/400), which will specify the order of
358 treatment group assignments. A patient is officially enrolled when the website
359 randomization process is completed.
360

361 **2.4.1 Delay in Randomization**

- 362 1. Visual acuity testing must be performed within 7 days prior to randomization. If patient
363 randomization is delayed beyond 7 days, the visual acuity testing must be repeated to confirm
364 eligibility and establish the baseline acuity for the study.
- 365 2. The ocular motility examination must be performed within 7 days prior to randomization. If
366 patient randomization is delayed beyond 7 days, the ocular motility examination must be
367 repeated.
- 368 3. No other parts of the examination (including the refraction) need to be repeated if they were
369 performed within 6 months prior to randomization.
370

371 **2.4.2 New Spectacles Prescription Upon Randomization**

372 All patients will be offered new, study-paid spectacles (frames and lenses) upon randomization.

373 The cost of all spectacle changes prior to randomization is not covered by the study.

- 374 1. For patients in whom the eyes are underplussed by more than +0.50 D spherical equivalent (but,
375 to be eligible, underplussed by no more than +1.50 D) upon randomization:
 - 376 • If the patient is randomized to the atropine only group, the prescription for both lenses in the
377 new frames will be exactly underplussed by +0.50 D spherical equivalent.
 - 378 • If the patient is randomized to the atropine plus plano lens group, the amblyopic eye lens
379 prescription will be exactly underplussed by +0.50 D spherical equivalent and the sound eye
380 lens prescription will be “plano”.
381

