4.4 Patient Withdrawals

A patient (and in this case the parents or guardian) may withdraw from the trial at any time. This is expected to be a very infrequent occurrence in this trial in view of the testing procedure's similarity to routine clinical practice. If the parents or guardian indicate that they want to withdraw the child from the study, the investigator personally should attempt to speak with them to determine the reason. If a plano group patient with high hypermetropia is intolerant to atropine and the plano lens, it is preferred that the patient wear his/her enrollment glasses and continue on atropine rather than withdraw from the study. The decision to restart the enrollment glasses should be discussed with a protocol chair.

Patients who receive alternate treatment, e.g. patching, for at least one week, will be dropped from the study after completion of the main outcome exam (8C).

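### Section 4.3 drops some randomized patients after a work-up triggered only by worsening acuity, without first obtaining the 18-week exam; this can cause a small, outcome-dependent loss of data

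*Protocol*

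**What the plan says.** Section 4.3 (Intercurrent Events) sets the trigger: "If visual acuity should worsen in the amblyopic eye (or in the sound eye and does not recover with cessation or reversal of treatment"). In that case "the investigator should evaluate this condition using best clinical judgment and perform whatever work up is clinically indicated", looking for a cause other than amblyopia. A patient with such a cause that "fully explains the visual loss (i.e., amblyopia was never present) will be dropped from the study". The section does not ask for an 18-week exam first.

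Three other places bear on this:

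- Section 2.4, item 1: "Once a patient is randomized that patient will be included regardless of whether the assigned" treatment is received. The next sentence tells the investigator to be sure that the parent will accept either regimen.
- Section 4.4, on patients given alternate treatment for at least a week: they "will be dropped from the study after completion of the main outcome exam (8C").
- Section 2.2, criterion 9: "No ocular cause for reduced visual acuity". Criterion 11 accepts an ocular examination up to 6 months old.

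Section 3.2.1 states masking for one visit only: "The visual acuity measurement at visit 8C (18 weeks) will be done by a masked" examiner. Section 5.2 defines the primary cohort by baseline acuity (20/40 to 20/100) and does not say how a patient dropped under 4.3 enters the ANCOVA.

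**The concern.** The 4.3 drop is in substance a late finding that an entry criterion was not met. Removing such patients can be defended if all patients are checked alike and without knowledge of arm. Section 4.3 provides neither. The check starts only when acuity has worsened, and acuity is the trial outcome. A child with the same missed condition who is stable or improves stays in. The decision rests on the investigator's judgment. That the investigator knows the arm is my inference, but a strong one, since the investigator prescribes the lenses and assesses compliance.

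The practical harm is the missing visit. Section 4.4 secures the 18-week acuity before a drop and 4.3 does not. A separate analysis plan can say how to handle a missing score, but it cannot recover an exam that was never done. If such drops fall unequally between arms, the 18-week comparison loses patients with poor results from one side.

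**Working it through.** **The two drop rules side by side**

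| | Section 4.3 | Section 4.4 |
|---|---|---|
| Trigger | Worsening acuity after randomization | Alternate treatment for at least one week |
| Condition | Other cause fully explains the loss; amblyopia judged never present | None further |
| Decided by | Investigator's judgment | Fact of treatment |
| 18-week exam before the drop | Not required | Required |
| Place in analysis | Not stated | Section 5.2 counts them as not reaching the better acuity in the 20/25 analysis |

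**The planned sample size, for scale.** Inputs from section 5.1: SD 0.16, correlation 0.40, two-sided alpha 0.05, power 90%, difference 0.075 logMAR, 5% loss. Equal allocation is my assumption.

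- Adjusted SD = 0.16 × √(1 − 0.40²) = 0.1466.
- The two-sample calculation gives 81 per arm. 81 / 0.95 = 85.3, so 86 per arm and 172 in total. This matches the protocol.
- Evaluable per arm after 5% loss: 172 × 0.95 / 2 = 81.7, about 82.

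**Shift in one arm's mean.** If k of n patients, each d logMAR worse than the arm's average, are lost, the mean of those remaining improves by k × d / (n − k). The protocol gives neither k nor d; both are assumptions. With n = 82:

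| k lost, one arm only | d = 0.2 | d = 0.5 |
|---|---|---|
| 1 | 0.2/81 = 0.0025 (3% of 0.075) | 0.5/81 = 0.0062 (8%) |
| 2 | 0.4/80 = 0.0050 (7%) | 1.0/80 = 0.0125 (17%) |
| 3 | 0.6/79 = 0.0076 (10%) | 1.5/79 = 0.0190 (25%) |

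Equal losses with equal deficits in both arms would cancel in the difference. The top corner needs three such children in one arm and none in the other, each 0.5/0.16 = 3.1 SDs worse than average.

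**Power.** With 163.4 evaluable patients, power is 90.5% at alpha 0.05. Losing 4 more brings it to 89.8%. The issue is possible bias, not sample size.

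**The case against.** Most of the case against a stronger reading stands.

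- **A flat contradiction with 2.4.** A reader might infer one from the words on inclusion. The clause goes on to speak of receiving treatment, and its context is parental acceptance of either regimen. Section 4.3 concerns patients judged never to have had the disease. The two sections need reconciling, but they do not plainly contradict each other.
- **Exclusion from analysis.** A reader might take the drop to mean this. Section 4.4 uses the same phrase for patients whom 5.2 still counts, so in this document it may describe follow-up only. Section 5 also points to separate documents for the detailed analysis. What remains is that, under 4.3, the data may not exist.
- **Removal of bad outcomes in general.** Worsening alone drops nobody; another cause must fully explain the loss. Eye injuries, and eye problems arising during the study, are only reported.
- **Removal of the sound-eye harm that the trial wants to measure.** This is tempting, because persistent sound-eye loss is a trigger and an earlier trial, cited in section 1.2, saw such loss at 6 months more "frequently when a plano lens was prescribed in addition to atropine (7 of 43, 16%) compared with" 4 of 123 (3%) on atropine alone. But the expected harm is reverse amblyopia (section 4.7.2), which is not a cause other than amblyopia and so does not meet the drop condition. Those figures do not show that 4.3 drops would differ by arm.

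It is also fair to say that keeping children without amblyopia in the primary analysis is debatable. My answer is that any exclusion should then rest on a check that does not depend on outcome or arm.

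**Conclusion.** The point holds as a limited design defect. As written, section 4.3 selects patients for a drop through worsening after randomization, states no masked adjudication, and does not secure visit 8C. The wording in parentheses is also loose: a cause that explains a loss seen after randomization does not by itself show that amblyopia was absent at baseline.

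The consequence is a possible small, outcome-dependent loss from the 18-week efficacy ANCOVA. A loss from the sound-eye analysis is less plausible. The illustrative range is 0.002 to 0.019 logMAR, or 3% to 25% of the target difference. It rests wholly on assumed counts and deficits, with all losses in one arm. Such cases are probably few, so the realistic effect is probably near the low end. The protocol does not show that a bias will occur, or which arm it would favour.

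**What to change.** Reconcile section 4.3 with 2.4 and 4.4:

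1. State in 4.3 that a patient with such a finding still has visit 8C, as 4.4 already provides for alternate-treatment patients.
2. State that the patient stays in the primary efficacy and safety analyses, and let 2.4 say that inclusion covers this case too.
3. Add a sensitivity analysis that excludes patients judged never to have had amblyopia. The judgment should be masked to arm and outcome and use pre-randomization information only.

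Treatment decisions stay as the protocol has them. The cost is a sentence or two of text, an 18-week exam for a few patients and one extra analysis. The downside is slight dilution of the treatment effect by a few children without amblyopia, which the sensitivity analysis would show.
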